- Keep the record of primary and secondary compensation updated.
- Match the identification number on the coupon to the participant's recruiter record.

Coupon Registration

- Record the date of the interview.
- Register the participant's questionnaire code.
- Record the participant's network size.
- Record the identification number of the coupon delivered to the participant.
- Record the identification numbers of the coupons given to the participant to recruit others.
- Record important notes or physical features.
- Record the initials of the interviewer.

Post-test advice

Given the serious ethical implications of developing diagnostic tests, the counseling process includes:

- Provide information and education about HCV.
- Referral to prevention, treatment, and support services. The local and departmental health secretary has previously been informed about this project for the correct identification of the support network and health services.
- Prior to this advisory process, a training session is held for the team responsible for collecting information.

Screening test

The samples are taken by the personnel assigned to the study with training to ensure the quality of the diagnostic process. At the appointment that is made, the rapid test is read to deliver the results.

The sample number will be linked to the survey through a code, which allowed confidentiality and anonymity to be maintained without losing the possibility of monitoring the results in order to return them to the subjects and offer the corresponding advice and follow-up. .

Delivery of results with their respective APV

With the results of the rapid HCV tests, counseling will be carried out after the detection test. The goal is to understand the outcome and provide appropriate information, support, and reference. If the result is negative, counseling offers an opportunity to promote behaviors that reduce infection risks; if the result is positive, to reduce the risk of transmitting the virus to other people. In addition, help must be given to face the result and its consequences on the person's personal life and that of the person's loved ones.

Training for interviewers

The interviewer will be trained in the application of the survey by the technical committee. Therefore, each one of them must attend the training to study the definitions and concepts well and to become familiar with the procedures and questions of the survey and ask questions about any procedure or content that is not clear and so on. Avoid errors as much as possible during field work.

Information processing

Automated processing will be carried out, the instrument will be designed, tabulated and its corresponding database created, tablets will be used with the survey application properly adjusted. The first analysis will be carried out in the RDSAT software⁴, a secondary analysis includes other packages such as STATA 10.0, SPSS version 27, with all these programs the statistical analysis of the data and the generation of output tables is carried out.

Results dissemination plan

At the end of the study, the results are shared and a report with publishable results is expected to be generated.

Social support for respondents in promoting inclusion and diversity

It is widely known that RDS is a sampling that requires using compensation bonuses that motivate the participation of a diverse group of PWIDs, and super-recruiters can be controlled and guarantee a close variance between the sample and a population estimate without a high homophily; The vouchers also allow you to cover travel expenses from one place to another, as well as the time invested to carry out the entire collection and sampling procedure.

As recognition, social support equivalent to \$40,000 Colombian pesos will be given for participation in the study process cycle and \$10,000 Colombian pesos for each recruited peer who was eligible and complied with the entire information collection process in the study. headquarters, for a maximum of three referrals per participating PWID, will be delivered after the administration of the survey and the collection of the blood sample for HCV.

Ethical considerations

The study protocol will be presented to the institutional human ethics committee of the CES University, which is recognized nationally.

⁴ Respondent Driven Sampling. Available at: <http://www.respondentdrivensampling.org/reports/RDSAT60.htm>. Accessed January 14, 2011.

The study complies with those established in Resolution 8430 of 1993 of the Ministry of Health of Colombia, according to its article 11 numeral b, it is classified as minimal risk, given that data records were used through common procedures consisting of a taking a blood sample by capillary and/or venous puncture. Furthermore, the criterion of respect for the dignity and protection of the rights and well-being of the participants will prevail.

Written informed consent will be requested from all participants, giving clear and easily understandable information about the objectives of the research. Questions about it will be explained and resolved, and complete freedom to withdraw consent will be given at any time during the study, because the subject considers (Annex 3).

The study will be coordinated by health professionals and the sampling and collection of information will be carried out by trained nursing assistants. The confidentiality of the data collected will be guaranteed, the information obtained will not be used for uses other than the current research process and at the time of disclosure of the information, no sensitive data or data that allows the identification of participating individuals will be published, the procedures will be followed. norms set out in law 1581 of 2012 on habeas data.

The application of rapid tests is governed by current regulations; in particular, by the guidelines for carrying out rapid tests outside the clinical laboratory for the early diagnosis of hepatitis C infection (Resolution 1314 of 2020 of the Ministry of Health and Social Protection).

In the development of this investigative process, the following ethical aspects will be considered by the researchers:

- The integrity of the people interviewed will be respected, regardless of risk behavior, by both the interviewers and the researchers.
- Interviewees will be informed of the terms of confidentiality in the informed consent. Written consent will be requested from the population to carry out the interview and take a blood sample, according to Resolution 8430 of 1993, which regulates research on living beings, according to article 14 of this same resolution, consent is understood. informed the written agreement, by which the research subject authorizes his or her participation in the research, with full knowledge of the nature of the procedures, benefits, and risk to which he or she will be subjected, with the capacity of free choice and without any coercion.

- In the attention of users, the same procedures will be carried out on all of them; it is important to highlight that these instructions will be the same for all users.
- The informed consent that will be signed by all the people who agree to participate in the study will clearly explain the justification and objectives of the research, the procedures that will be carried out, which will also indicate that there are no relevant risks and the benefits that can be obtained; In addition, the guarantee of receiving an answer to any question and clarification of any doubt about the research and other matters related to the topic and finally the freedom to withdraw your consent at any time and stop participating in the study without thereby create harm in their social environment.
- Since the sample is blood, it will be guaranteed to have qualified personnel to take samples, as well as guarantee all biosafety procedures and proper handling of blood samples.
- The identification number will be linked to the name, telephone number or contact information of the person in a database to which only the study coordination and field work supervision will have access.
- This study is also governed by the provisions of Chapter IV of Decree 1543/97, which establishes: With respect to the right to autonomy, which is none other than self-determination in the full right of the person's faculties, freely and spontaneous for the benefit of the development of their personality, it was very important to include that the practice of the diagnostic test for the detection of antibodies against HCV requires the informed consent of the person, a requirement without which it cannot be carried out.
- The same Decree establishes the obligation to offer counseling (Article 5). And along the same lines, article 6 establishes that the results of tests for diagnosing HCV infection and those for diagnosing sexually transmitted diseases (STDs) must be delivered to the patient by personnel duly trained in counseling.
- There are suitable personnel in the areas that involve the topics of the study, with knowledge and experience to take care of the integrity of the human being to guarantee the well-being of the research subject.
- The privacy of the individual will be protected, identifying them only when the results

require it and they authorize it.

- In relation to confidentiality, Article 34 of Decree 1543/97 establishes that members of the health team who know or provide health care to an infected person are obliged to keep the consultation, diagnosis, and evolution of the disease confidential. and all the information that belongs to your privacy.
- All possible types of risk and the possibility that the research subject will suffer harm as an immediate or delayed consequence of the study will be identified.
- Subject participation will be entirely voluntary.
- The cases of other people who have had risky sexual contact and who are not a key population of the study, will be notified according to the public health surveillance protocol. These actions will be coordinated for this purpose with the territorial entity and specifically with the secretaries of health, the latter will be informed from the beginning of the project about the scope of the research and the actions that will be carried out; positive cases will also be notified within the public health surveillance system of the corresponding entity.

None of the authors have conflicts of interest to declare.

Expected results and impact

Strengthening the scientific community

Expected result/product	Indicator	Beneficiary
Screening for hepatitis C in PWID.	Proportion of PWID with a diagnosis of hepatitis C.	PWID, users affiliated with the SGSSS, benefit plan administrative entities, health personnel.
Linkage to the treatment of confirmed positive cases for HCV infection at the site included in the study.	Proportion of PWID with a diagnosis of chronic hepatitis C who started treatment.	PWID, users affiliated with the SGSSS, benefit plan administrative entities, health personnel.

Social appropriation of knowledge

Expected result/product	Indicator	Beneficiary
Circulation of specialized knowledge: Presentation of results at scientific events (national and international).	Participation in scientific events presenting research results.	Medical-scientific community, decision makers, hospital institutions.
Presentation of results to stakeholders of the Colombian SGSSS.	Participation in an event with different stakeholders of the SGSSS.	Insurers and providers, nationwide. SGSSS patients

Generation of new knowledge

Expected result/product	Indicator	Beneficiary
Research article submitted to a journal indexed in one of the bibliographic citation indexes such as, for example, ISI-Web of Knowledge (Science Citation Index [SCI] and Social Sciences Citation Index [SSCI]) or SCOPUS, Publindex, Lilacs, BVS, Latin index, among others.	Published scientific articles.	Medical-scientific community, decision makers, hospital institutions.

Expected impacts from the use of the results

Expected impact	Term (years) after project completion*	Verifiable indicator	Assumptions*
Improvement in the opportunity to detect new cases of hepatitis C among PWID.	1-4 years	Increase in the incidence rate for hepatitis C.	Medical personnel adherent to the screening and diagnosis algorithm – applicability of this among PWID.
Improvement in the times elapsed between confirmatory diagnosis with PCR and the start of treatment.	1-4 years	Increase in the route that allows a diagnosis of chronic stages for the hepatitis C who diagnosis, treatment, started treatment.	Standardization of the number of PWID with compliance with all stages for the hepatitis C who diagnosis, treatment, and monitoring of PWID with HCV.
Successful completion of treatment between PWID	1-4 years	Increase in the proportion of PWID with up, adherence of cure (sustained viral response).	Opportunity in follow-up, adherence of PWID to the treatment scheme.

Expected impact	Term (years) after project completion*	Verifiable indicator	Assumptions*
Changes in the prevalence figures of chronic hepatitis C among PWID.	5-9 years	Trend in crude prevalence of chronic hepatitis C.	Early detection and treatment reduce the risk of transmission.

short (1-4), medium (5-9), long (10 or more)

Schedule of activities

The activities will be executed in 10 months, the first two months of planning the activities, carrying out and submitting the protocol, selecting the field team, two months in the design, and execution of the exploratory phase, including the delivery of the unique object; the following four months of field activities, and the following two months for the delivery of results, and analysis of information, including the reproduction of the final document.

Activities	Start date	Final date
Development of the final protocol, consent reports and approval by the ethics committee.	Month 1	Month 1
Nursing personal training for information capture, sample collection, referral to treatment and follow-up.	Month 2	Month 2
Development phase 1 exploratory component.	Month 3	Month 4
Recruitment of participants – Identification of risk populations to be screened – Screening tests – entry of captured information.	Month 5	Month 7
Monitoring of positive cases –	Month 8	Month 8

Activities	Start date	Final date
treatment route direction.		
Verification of the quality of the information collected.	Month 5	Month 8
Analysis of data.	Month 9	Month 9
Final report presentation.	Month 10	Month 10
Writing and presenting article for publication.	Month 10	Month 10

Human resource

Activities of the city supervisor

Armenia will have a supervisor, who must guarantee that all the procedures defined for field work and completion of the survey are fully complied with. With a professional profile, preferably with postgraduate training in the areas of public health, epidemiology and/or related.

Staff activities

This is the person who is responsible for collecting information in the PWID. To reach the sample proposed in the study protocol, it is required that the interviewer be committed to his or her work, clearly know the functions he or she must perform, be a responsible, orderly, accomplished person, and have certified experience. of work, in addition to having the ability to generate empathy and trust, and to demonstrate that they have the basic knowledge necessary to contribute to the fulfillment of the objective of the study and to pass the evaluation after the training.

Principal investigator career

[name]. Medical specialist in Internal Medicine, Gastroenterology and Digestive Endoscopy, Master in Liver Diseases and Clinical Epidemiology. University Research Professor, president of the Colombian Association of Hepatology (2021-2023). Active participant in the working groups of the National plan for the elimination of Viral

ID: CO-US-987-7106 - Version May 2024

Hepatitis, national lecturer on Viral Hepatitis B and C, former public health advisor to the District Health Secretary of Santa Marta, extensive experience in viral hepatitis screening activities in the community, co-author of the Colciencias project - CALL 777: Prevalence and modeling of Hepatitis C Virus infection in Colombia.

Budget

This project will be carried out by the Colombian Association of Hepatology (ACH), it corresponds to an initiative of the ACH in response to its commitment to join efforts to achieve the World Health Organization's goal of eliminating viral hepatitis by 2030. and is financed with resources from the ACH, which in turn are obtained by the association's own activities and resources obtained from calls for project financing. Leadership in communication and administration of project resources is provided by the ACH.

A final project report will be generated, and the results will be maintained in a consolidated and anonymized manner, without compromising confidential information of the participants.

The ACH is the author of the project, it will provide the resources for its execution. The items covered in the execution of the study do not include the costs of treatment or any clinical management procedures (for example, doctor visits, follow-up laboratories) since they are part of the usual treatment for hepatitis C virus infection. and it is contemplated in Colombian regulations that once the confirmed case of hepatitis C is notified to SIVIGILA (file 340), on a quarterly basis the High-Cost Account downloads that information, includes the participant in the national cohort of high-cost diseases. Hepatitis C establishes communication/audit with the Benefits Plan Administration Company (EAPB) to which the user belongs and guarantees their connection to the treatment, treatment against hepatitis C that is free, without cost for the EAPB or out-of-pocket expense for the user. user and which is acquired in annual purchases by the CAC since 2017 through the centralized purchasing mechanism from the Pan American Health Organization.

Annexes

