Population size (for finite population correction factor or fcp) (N): 580¹

Hypothetical % frequency of the outcome factor in the population (p): 77.80%²+/-5

Confidence limits as % of 100 (absolute +/-%) (d): 5%

¹Patients treated at the Armenia City Listening Center between 2016-2023.

²Estimated based on the 2021 prevalence (62.80%), along with the growth speed of 5% per year.

Design effect (for group surveys-EDFF): 1

Sample size (n) for various confidence levels.

Interval Trust (%)	Size of the sample
95%	186
80%	98
90%	145
97%	213
99%	260
99.9%	331
99.99%	377

Sample size n = $[EDFF^*Np(1-p)] / [(d^2/Z^2(1-\alpha/2)^*(N-1) + p^*(1-p))]$

Source: Results from OpenEpi, version 3, the SSPropor open-source calculator

The sample size may vary by up to 10%, taking into account (i) the methodological adjustments that are made once the study begins, in which case the sample size will be adjusted.

Sample size 205 individuals.

Sample design

Due to the type of population (PWID), it is not possible to have a known sampling frame that allows designing a conventional probabilistic sample, so a chain reference sample will be taken based on those who respond (respondent driven sampling -RDS), a method that has proven its usefulness to access hard-to-reach populations (15,16). Respondent-driven sampling is a network-based sampling method, which makes it possible to draw statistically valid samples from previously unreachable groups. It is based on long referral chains and therefore several waves of recruitment. Likewise, several waves of recruitment make it possible to ensure that the final sample is independent of the seeds and this sample is similar to the population of the network from which the sampling was done (16). For example, in the prevalence study in 2021, the method estimated a population of 463 (95% CI: 431-497) people who inject drugs. Regarding completeness, through the RDS methodology, 53.4% of the population were identified and the method estimates that 80.19% of the population in the city of Armenia was identified³ (16).

The seeds are those leaders of the population who begin the information gathering process.

³<https://www.minjusticia.gov.co/programas-co/ODC/Documents/Publicaciones/Informe%20de%20Resultados%20de%20Investigaci%C3%B3n%20n%20PID%20Armenia-Cu%C3%81cuta%20Marzo%202022.pdf>

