In this sampling it is necessary to link the referral with the interviewee, which is achieved through coupons marked with the RDS code (unique number) that allows identifying all the referrals of a seed and therefore its social network. Likewise, the reference quota is controlled with a maximum number of coupons, which for this study would be three per interviewee, which allows limiting "recruiter" bias; coupons are an inclusion criterion that allows determining whether the person was eligible for participate and essential to preserve the link between referent and referred.

Respondents recruit their peers, as in network-based samples, and researchers keep track of who recruited whom and their number of social contacts. A mathematical model of the recruitment process then weights the sample to compensate for non-random recruitment patterns. This model is based on a synthesis and extension of two areas of mathematics, first-order Markov chain theory (i.e., sampling occurs with replacement, the sample becomes independent of the seeds). And biased network theory, which were not part of the standard toolset of mathematical sampling theory. The resulting statistical theory, called RDS, allows researchers to provide unbiased population estimates and measures of the precision of those estimates.

Variables

The dependent variable would be the identification of HCV antibodies, which is qualitative with nominal measurement as presence (positive) or absence of the virus (negative). The questions that will make up the survey will be the independent variables, whose nature is qualitative or quantitative and the measurement levels are nominal and ratio, such as age, number of times per day in which you inject, number of people with whom you have shared syringes and needles, injection equipment, number of casual or commercial couples, among others.

Collection of information and sampling procedure

Once approval has been obtained from the research ethics committee for this study, in the first phase people called seeds are selected, a record of the identified population will also be made, and the first part of the capture-recapture methodology will be applied. In the second phase of expansion, it is expected to recapture the population and estimate the population, with which the waves of the RDS methodology are carried out.

The researcher initially searches for individuals (called seeds) who belong to the population

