The RDS itself estimates the sampling errors described through measures such as homophily, heterophily, and proportional estimates of the population. Initially, homophily will be calculated, which describes the extent of the ties of the social network inside or outside it. The homophily/heterophily scale is between 1 and -1, where 1 indicates that all participants with certain characteristics invited someone with the same characteristics, while -1 indicates that all participants with a certain characteristic invite someone with one characteristic opposite or different; 0 (zero) was the point at which participants randomly invited other individuals from the population of all possible invitees.

The RDS technique uses the information available in the sample about the social network to obtain asymptotically unbiased estimators of the proportions of the population in the different groups in which they want to be characterized. These estimators are called population prevalence estimators.

Descriptive statistics (frequencies and percentages) will be estimated. For continuous quantitative variables, measures of central tendency (average and median) and measures of dispersion (variance, standard deviation) will be estimated.

A descriptive analysis of the characteristics of the population under study will be carried out, according to the socio-demographic variables: sex, age, educational level, stratum, insurance, in addition the prevalence of HCV and the proportions of the sample and the population will be obtained. according to the risk behavior variables associated with infections. All these analyzes are carried out by estimating the population with their corresponding 95% confidence intervals.

Possible relationships between sociodemographic variables, risk factors and documentation of positive antibodies for HCV will be explored. For this purpose, a bivariate analysis will be proposed using chi-square tests to explore the proposed associations. The test allows us to determine, for each pair of variables, the existence or not of the relationship through the difference between the value that should result if the two variables were totally independent, and the one observed in the data. The greater the difference, the greater the relationship between the variables.

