The significance between the relationships will be determined by the p-value of the test, a value less than 0.05, it is accepted that there is a statistical association between the two variables analyzed.

The processing will be carried out in the RDSAT® version 5.6 program.

C. WORK PLAN

Phase 1. Exploratory component

With the purpose of making an approach and identifying barriers to the study and possible alternative solutions to consumption contexts, as well as establishing inter-institutional alliances that facilitate communication with research subjects called seeds, an exploratory phase will be carried out through the use of a qualitative technique that enables the collection and construction of data that enriches the information obtained by the subsequent application of the structured survey that underpins the present study.

We will seek to identify characteristics of the social network: subgroups, connectivity, personal network, the acceptability of the study, interest, possible reasons for not

ID: CO-US-987-7106 - Version May 2024

participating, as well as define logistical aspects, such as the site for collecting information, schedules, coupon design and the profile of the personnel who will serve the prioritized populations.

Through interviews with representatives of various institutions in Armenia who, from research, care, and treatment, offer the research team a general overview of the context and care routes; and from there provide elements that guide field work and the analysis of the information obtained from the surveys.

After prioritizing institutions, they will be inquired about the description of the problem, characterization of the populations, institutional experiences, research, territorial location, methods of approach, risk behaviors and practices for HCV infection, among others. The estimated time to complete the exploratory phase will be two months, this includes the collection, analysis and interpretation of the data and the understanding of the conditions found.

Interviews with key informants

These people are considered experts in the social and cultural context of PWIDs, with the objective of understanding the context and behavior of users; example of key informants: people who have worked with populations, people from institutions, NGOs, among others. In this first phase, the capture technique, already described previously, will also be applied.

Phase 2. Quantitative component

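### The ±5-point precision relies on a finite population correction at N=580, but the written RDS model is with replacement; under that model 205 people give about ±5.7 points at best

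*Protocol*

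**What the plan says.** Protocol section B, Target population size, lists the inputs to the calculation:

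- "Population size (for finite population correction factor or fcp) (N") is 580. Its footnote describes this as patients treated at one listening centre in Armenia between 2016 and 2023.
- "Hypothetical % frequency of the outcome factor in the population (p): 77.80"%, with a margin of 5 points either side.
- "Confidence limits as % of 100 (absolute +/-%) (d): 5"%.
- "Design effect (for group surveys-EDFF): 1".

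The formula printed beneath contains N−1, so the correction is built in. The table gives 186 at 95% confidence, and the section ends with a sample of 205.

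The Sample design section then describes the model that weights the sample. It rests on "first-order Markov chain theory (i.e., sampling occurs with replacement, the sample becomes independent of the seeds"), and this theory is said to supply both the population estimates and their precision. The Data analysis plan adds: "All these analyzes are carried out by estimating the population with their corresponding 95% confidence intervals". It also says: "The processing will be carried out in the RDSAT® version 5.6 program". The Information processing section makes RDSAT the first analysis and lists STATA and SPSS for a secondary one.

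The Sample design section also cites the 2021 study, in which "the method estimated a population of 463 (95% CI: 431-497) people who inject drugs".

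**The concern.** The correction shrinks the variance because a large share of a small population is sampled without replacement. A with-replacement model gives no such credit. The protocol takes the credit when it sets the sample size and then describes an analysis whose stated theory does not allow for it. Population size appears elsewhere as an objective in its own right, estimated by capture-recapture, but no section says that the estimate enters the prevalence interval.

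The stated precision is the only justification given for the sample size, and anti-HCV prevalence is the main quantity the study is meant to deliver. If the analysis follows the model as written, the printed ±5 points describes a different procedure from the one that will produce the interval. This holds with the design effect left at exactly 1, so it is separate from any question about network clustering.

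The choice of 580 also looks odd. The Population section defines the universe as people aged 18 to 65 who injected in the last six months, whereas 580 is a cumulative client count over eight calendar years at one centre.

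**Working it through.** **Inputs.** N=580, p=0.778 (range 0.728 to 0.828), d=0.05 and design effect 1, all from Target population size; z=1.96 for the 95% intervals of the Data analysis plan; N=463 (431 to 497) from Sample design; p=0.696, the 2021 Armenia figure in the Problem statement.

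**1. Reproduce the plan's figure.** n = N·p(1−p) / [(d²/z²)(N−1) + p(1−p)].

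- p(1−p) = 0.778 × 0.222 = 0.172716.
- (0.05²/1.96²) × 579 = 0.37679.
- n = 580 × 0.172716 / (0.37679 + 0.172716) = 182.3, so 183.

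The table prints 186. Using p=0.77 gives 186 and also returns the other six table entries exactly (98, 145, 213, 260, 331, 377), so p was probably entered as 77%. The gap is immaterial here, and the table is clearly the corrected formula at N=580. The 205 fits the 10% allowance: 186 × 1.10 = 204.6.

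**2. Remove the correction.** n = z²·p(1−p)/d² = 3.8416 × 0.172716 / 0.0025 = 265.4, so 266.

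**3. Half-widths at p=0.778.** Without correction: 1.96·√(p(1−p)/n). With correction: the same × √((N−n)/(N−1)).

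- n=205, without: 1.96 × √(0.172716/205) = 5.69 points. With N=580: 5.69 × √(375/579) = 4.58. With N=463: 5.69 × √(258/462) = 4.25.
- n=186, without: 5.97 points. With N=580: 5.97 × √(394/579) = 4.93.

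An uncorrected interval of ±5 points at n=205 has z = 0.05/0.02903 = 1.72, which is about 91.5% confidence.

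**4. Other prevalences, n=205, design effect 1.**

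| p | No correction | Correction, N=580 |
|---|---|---|
| 69.6% | ±6.30 | ±5.07 |
| 72.8% | ±6.09 | ±4.90 |
| 77.8% | ±5.69 | ±4.58 |
| 82.8% | ±5.17 | ±4.16 |

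Without the correction, ±5 is missed across the whole stated range of p.

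**5. Effect of N on the required n (formula in step 1, p=0.778).** N=431: 164.5. N=463: 168.9. N=497: 173.2. N=580: 182.3. A smaller N lowers the requirement.

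**The case against.** The strongest reply is that recruitment really is without replacement. The Instructions for recruitment do not count a referral who has already taken part, and 205 is 35% of 580 or 44% of 463. On that view the correction in the sizing fits the fieldwork, and the with-replacement phrase is only background theory. Much of this stands: the true sampling error may well be below ±5.7. It does not remove the conflict, because the protocol says that the with-replacement theory is the source of its precision measures.

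A second reply is that the variance estimator may be set in an analysis plan that is not shown. That is possible. But an estimator that uses N would depart from the model the protocol describes, so the protocol text would still need to be reconciled with it.

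Three stronger readings are tempting, and the documents do not support them.

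- *The reported interval will be about a quarter wider than planned.* The ratio 5.69/4.58 = 1.24 assumes a simple binomial variance. The documents do not say how RDSAT computes intervals, so this is what the written model implies at design effect 1, not a forecast.
- *The choice of 580 causes the shortfall.* It works the other way: 580 gives a larger required n than 463.
- *The 2021 interval of 431 to 497 rules out 580.* The passage is ambiguous. It goes on to say that 80.19% of the city's population was identified; if 463 is the identified part, the total is 463/0.8019 = 577.

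It is also fair to say that the design effect may matter more. The documents give no value above 1. At an assumed 1.5 or 2, the uncorrected half-width at 205 would be 5.69 × √1.5 = 6.97 or 5.69 × √2 = 8.05 points.

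**Conclusion.** The concern holds as an inconsistency between the sizing model and the written analysis model. Under the with-replacement model, the target is missed by about 0.7 points at p=77.8%, by 0.2 to 1.1 points over the stated range of p, and by 1.3 points at 69.6%. These figures assume a simple binomial variance and design effect 1. They also take the analysis to be as written, since no section applies a correction.

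Under a finite-population analysis, 205 meets ±5 at the stated p for either N. A reader might infer that recruitment should rise to 266; that does not follow, because the shortfall depends on which model is used and the plan has not settled this. The mismatch between 580 and the six-month universe is an input to reconcile, not a reason why the precision fails. Overall this is a modest but real correction to the one precision statement behind the sample size.

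**What to change.** Keep 205 and make sizing and analysis use the same sampling model, in one of two ways.

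1. Keep the with-replacement model. Drop the correction and state the precision as about ±5.7 points at best at p=77.8% (±6.3 at 69.6%), for design effect 1, noting that any network design effect widens it. This changes wording only and needs no extra participants; the cost is a less favourable stated precision.
2. Keep the correction. Specify a without-replacement RDS estimator, of the successive-sampling type, that takes N as an input. Define N as people who injected in the last six months, explain or replace 580, and show the interval over a range of N, for example 431 to 580, and then at the study's own capture-recapture estimate. This costs a change of estimator, possibly of software, and one sensitivity table.

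Either way, the Sample design section and the Data analysis plan should say whether N enters the prevalence interval.
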